8.3 Vital Signs and Weight

Weight and vital signs (including systolic blood pressure, diastolic blood pressure, pulse rate, and body temperature) will be summarized overall. Descriptive statistics of each parameter at baseline will be provided along with the change from baseline at each subsequent visit. A subject-level listing will also be provided.

8.4 Physical Examination

Results of the general physical and knee examinations were noted in the source documents. If any clinically significant finding was noted after study medication injection, it was to be reported as an AE.

9. MEDICATIONS

The summary of medications will be performed on the SAS.

9.1 Concomitant Medication

The World Health Organization Drug Dictionary (WHODD) will be used to classify prior and concomitant medications by Anatomical Main Group (Anatomical Therapeutic Chemical, ATC, Level 1), Therapeutic Subgroup (ATC Level 2), and preferred term. Prior and concomitant medication usage will be summarized by the number and percentage of subjects receiving each medication overall.

The subgroup of medications initiated after first exposure to study product will be summarized in the same manner. If a medication start or end date is incomplete, it will be imputed in a way that assumes maximum exposure time (see table below).

Partial Date Availability	Impute Start Date		Impute End Date	
Year (YYYY)	Prior to Injection year	YYYY-12-31	Prior to end of study year	YYYY-12-31
	Same as Injection year	Injection Date	Same as end of study year	End of Study Date
	After Injection year	YYYY-01-01	After end of study year	YYYY-01-01
Year and Month (YYYY-MM)	Prior to Injection year and month	YYYY-MM-[DD, last day of month]	Prior to end of study year and month	YYYY-MM-[DD, last day of month]
	Same as Injection year and month	Injection Date	Same as end of study year and month	End of Study Date
	After Injection year and month	YYYY-MM-01	After end of study year and month	YYYY-MM-01
Ongoing or unknown status at end of study (e.g., no end date and unknown whether ongoing)	Not Applicable		End of Study Date	

Additional Considerations	If the end date is not missing, and the imputed start date is after the end date, the start date will be set equal to the end date.	If the imputed end date is before the start date, then the imputed end date will be set equal to the start date.
---------------------------	---	--

Subject-level listings containing prior and concomitant medications (WHODD coding), and procedures/non-drug therapies (MedDRA coding) will be provided and will display the dates as they were entered (not the imputed version described above).

9.2 Exposure and Compliance

A subject-level exposure listing will be provided.

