2. INTRODUCTION

2.1 STUDY RATIONALE

Clinical studies of LOR to date have only administered LOR into one knee (the “target knee”) and on a fixed schedule (given once, given once every 6 months, or given every 12 months). In addition, in previous safety and efficacy studies, other injectable agents, specifically glucocorticoids and hyaluronic acid (HA), were prohibited. This study is being conducted to gain an understanding of how LOR is used when the previous clinical trial restrictions (i.e., unilateral use only, fixed injection schedule, and use with other agents) are removed, which should be more representative of real-life clinical practice if LOR were to be approved. This study will also provide information about safety and efficacy with longer-term use, as LOR has not previously been used in studies of more than 2 years in duration.

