7.5 CONCOMITANT MEDICATIONS, TREATMENTS, AND PROCEDURES

Details regarding the name, indication, route of administration, dose, and frequency of all medications taken within 30 days prior to the Screening Visit through Month 36 (EOS)/ET will be recorded in the “Prior and Concomitant Medications” eCRF. “All medications” should include prescription, over-the-counter, supplements, and herbal or alternative medications, as well as glucocorticoid and HA injections for indications other than OA.

Procedures or non-drug therapies that are ongoing, new, or modified at or after the Screening Visits must be recorded on the “Procedures and Non-Drug Therapies” eCRF.

AE assessments should include consideration of any new or modified concomitant therapies administered to the subject.

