10.4.3 ANALYSIS OF THE EFFICACY ENDPOINTS

Change over time in the efficacy endpoints will be characterized for each knee and each medication using a pre-injection adjusted analysis of covariance (ANCOVA) with time and pre-injection value as covariates. Unadjusted 95% confidence intervals and *P* values will be reported for the estimated change over time from pre-injection. Percentage of subjects achieving 30%, 50%, and 70% improvement will also be summarized over time from pre-injection.

Frequency and interval of time between injections will be summarized by medication and subsequent number of injections. Efficacy will be characterized by study medication and injection number.

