10.5 SAMPLE SIZE

The sample size is not based on statistical considerations. A sample size of 300 subjects is a reasonable sample size to observe patterns of use of LOR and other IA injections.

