3. STUDY OBJECTIVES AND ENDPOINTS

3.1 Study Objective

The objective of this study was to determine the efficacy, safety, and tolerability of the SM04690 Injectable Suspension 0.07 mg alone and in addition to other standard of care intra-articular (IA) treatments in subjects with knee OA.

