3.2.2 Efficacy Endpoints

1. Change from baseline in pain numeric rating scale (NRS) score for the knee at Month 3 and annual visits, at each Unscheduled Injection Visit, and 3 months after each injection
2. Change from baseline in Western Ontario and McMaster Universities Osteoarthritis Index (WOMAC) physical function subscore (WOMAC Function) at Month 3 and annual visits, at each Unscheduled Injection Visit, and 3 months after each injection
3. Change from baseline in WOMAC total score and pain and stiffness subscores at Month 3 and annual visits, at each Unscheduled Injection Visit, and 3 months after each injection

4. Change from baseline in the Knee Injury and Osteoarthritis Outcome Score (KOOS) subscales of Symptoms, Function (Sports), and Quality of Life at Month 3 and annual visits, at each Unscheduled Injection Visit, and 3 months after each injection
5. Change from baseline in HRQoL (as measured using the 12-Item Short Form Health Survey [SF-12]) and Work Productivity and Activity Impairment (WPAI) at Month 3 and annual visits
6. Patient-Acceptable Symptom State (PASS) at Month 3 and annual visits
7. Change from baseline in 40-meter walk test time at Month 3 and annual visits, at each Unscheduled Injection Visit, and 3 months after each injection (at a subset of sites)
8. Change from baseline in the Timed Up and Go (TUG) test time at Month 3 and annual visits, at each Unscheduled Injection Visit, and 3 months after each injection (at a subset of sites)
9. Frequency of and interval between knee IA injections

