10. CHANGES TO PLANNED ANALYSIS

Change	Protocol Section	Rationale
Analysis of the AEs and clinical laboratory evaluations will not be performed. All available safety data will be listed.	10.4.2	Limited available data. See section 8.1 and 8.2.
Analysis of the efficacy endpoints will not be performed. Available efficacy data will be listed.	10.4.3	Study was terminated early.

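### Cancelling the efficacy analyses also cancels the injection-pattern summary, the protocol's third secondary objective and only sample-size reason, with no reason specific to it

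*SAP*

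**What the plan says.** Protocol 2.1 opens its rationale this way: "This study is being conducted to gain an understanding of how LOR is used when the previous clinical trial restrictions" are lifted. It adds longer-term safety and efficacy as a second reason. Protocol 3.1 makes safety and tolerability the primary objective, for LOR both alone and alongside other intra-articular treatments. Treatment patterns of LOR, glucocorticoid and HA in both knees are the third secondary objective. Protocol 10.5 disclaims any statistical basis for the sample size and gives one reason: "A sample size of 300 subjects is a reasonable sample size to observe patterns of use of LOR and other IA injections".

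The endpoint that carries this objective is number 9 in the efficacy list of both documents: "Frequency of and interval between knee IA injections". Its planned analysis is in protocol 10.4.3: "Frequency and interval of time between injections will be summarized by medication and subsequent number of injections".

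SAP 3.1 begins "The objective of this study was to determine the efficacy, safety, and tolerability of the SM04690 Injectable Suspension 0.07 mg alone" and goes on to cover use with other intra-articular treatments, but it does not mention treatment patterns. SAP section 10 disposes of protocol 10.4.3 in one row: "Analysis of the efficacy endpoints will not be performed. Available efficacy data will be listed". The stated rationale is early termination. SAP 9.2 consists of "A subject-level exposure listing will be provided". SAP 5.1 keeps data from unscheduled visits out of summary tables. SAP 6.3 tabulates LOR treatment on Day 1 and OA laterality.

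**The concern.** Endpoint 9 needs no patient-reported outcome. It needs injection dates, products, knees and the end of observation. Termination for business reasons (SAP section 4) explains why change scores at Months 12 to 36 are lost. It does not explain why injections already given should go uncounted, and neither SAP section 7 nor section 10 addresses that. The cancellation seems to follow from where the endpoint is filed rather than from a decision about it.

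Two things are at stake. The study would end without a summary on its lead question. The primary objective also distinguishes LOR alone from LOR with other injections, so the 2 reported adverse events (SAP 8.1) cannot be read against it without the number of subjects in each category and the time they were observed.

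**Working it through.** **1. What is tabulated and what is not**

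| Quantity | Planned summary table | Otherwise |
|---|---|---|
| LOR on Day 1 | Yes, SAP 6.3 | listing |
| LOR after Day 1, by knee | None | SAP 9.2 listing |
| Glucocorticoid or HA given for OA | None certain | SAP 9.2 listing, if it covers them |
| LOR alone versus LOR plus glucocorticoid/HA | None | to be worked out from listings |
| Person-months observed | None | to be worked out from listings |

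Two other routes are narrow. Unscheduled Injection Visits are a main occasion for repeat injections, and later injections of an HA series are entered as Unscheduled Visits (protocol 4.1.1); read literally, SAP 5.1 excludes both from tables. The medication form described in protocol 7.5 covers all medications "as well as glucocorticoid and HA injections for indications other than OA", which suggests that injections for OA are recorded elsewhere. The SAP 9.1 summary may therefore miss them.

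**2. The figure of 300**

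It cannot be reproduced, because no precision target, effect or power is stated. For scale, the 95% half-width of a proportion, 1.96 × √(p(1−p)/300), is 3.4, 5.2 and 5.7 percentage points at p = 0.1, 0.3 and 0.5. This describes the planned size; the documents do not give the number treated.

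**3. What early termination leaves observable**

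SAP 8.2 says that no subject completed a post-baseline laboratory visit. The first such visit is Month 12, Day 360 ± 28, that is Days 332 to 388. Follow-up therefore appears to have been under about 12 months. This is an inference and not certain, since the protocol's early termination (ET) visit also includes laboratory sampling. The 6-month minimum limits only repeat LOR in the same knee. LOR in the other knee is allowed after Day 1, and glucocorticoid or HA from Month 3 (protocol 4.1.1), so injection counts are meaningful even with short follow-up.

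**4. Why intervals need censoring if they are reported**

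Assumption, not in the documents: the same-knee LOR interval is T = 6 + an exponential delay with mean m months. An interval is complete by cut-off C if T ≤ C. With L = C − 6:

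- share completed = 1 − exp(−L/m)
- mean of completed intervals = 6 + m − L·exp(−L/m) / (1 − exp(−L/m))

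Example, m = 12 and C = 12: L = 6 and exp(−0.5) = 0.607. The share completed is 0.393, and the mean is 18 − 6 × 0.607/0.393 ≈ 8.75, against a true mean of 18.

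First intervals, in months; the last two columns are simulated with C uniform on 6 to 12 months:

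| m | True mean | Completed, C = 33 | Completed, C = 12 | Share, C = 12 | Completed, C 6–12 | Share, C 6–12 |
|---|---|---|---|---|---|---|
| 3 | 9 | 9.0 | 8.1 | 87% | 7.4 | 57% |
| 6 | 12 | 11.7 | 8.5 | 63% | 7.7 | 37% |
| 12 | 18 | 14.8 | 8.8 | 39% | 7.8 | 21% |
| 24 | 30 | 17.0 | 8.9 | 22% | 7.9 | 12% |

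Over the full 33-month injection window the bias runs from nil to large. After a cut-off at 12 months or earlier the result is nearly the same whatever the truth, because it is held between the 6-month minimum and the cut-off. Breaking results down by injection number, as protocol 10.4.3 does, adds a false trend: with m = 6 over 33 months, simulated completed intervals 1 to 4 average 11.7, 10.7, 9.2 and 7.7 months with no real change.

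Kaplan-Meier with open intervals censored at 12 months gives medians of 8.1 and 10.2 for m = 3 and 6, equal to the true values 6 + m·ln 2. For m = 12 and 24 (true medians 14.3 and 22.6) it reports the median as not reached. The completed-interval medians are 7.7, 8.3, 8.6 and 8.8.

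**The case against.** The best defence is that the change is open and proportionate. SAP section 10 discloses it with a reason, the protocol itself files endpoint 9 under efficacy, SAP 3.2.2 still lists it, and a dated exposure listing lets a reader count injections. With so little data there may be almost nothing to summarise, and few or no same-knee LOR intervals.

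Much of this stands, and it rules out several stronger readings:

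- A reader might infer that the endpoint was dropped silently. It was not; what is missing is a reason that applies to it.
- A reader might infer that no table shows who received LOR. SAP 6.3 tabulates Day 1 treatment.
- A reader might infer that glucocorticoid and HA given for OA will certainly go uncounted in SAP 9.1. Protocol 7.5 supports only that they may.
- A reader might infer that use patterns were the sole rationale. Protocol 2.1 also names longer-term safety and efficacy.
- A reader might infer that the trial will report a biased interval. The SAP no longer runs that summary. Protocol 10.4.3 never restricts it to completed intervals, and protocol 10.1 leaves the details to the SAP. Plain descriptive statistics with no rule for open intervals invite the error but do not prescribe it.

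The argument from sparse data does not carry the rest. The SAP still tabulates vital-sign changes, baseline characteristics and concomitant medications, and a short injection table is no harder. If no knee was re-injected, a table with person-months says so directly.

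**Conclusion.** The point holds as a gap in reporting. An endpoint that carries a secondary objective, the lead rationale and the only sample-size reason loses its summary through its filing under efficacy, with no reason particular to it. Day 1 LOR aside, later injections, treatment combinations and observation time reach the reader at most through listings. Correcting this is a cheap improvement; the omission does not bias any analysis now planned.

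The censoring result is a caution for anyone who reinstates the interval summary. The downward direction follows from leaving out knees not yet re-injected. The size depends wholly on the assumed delay: with a 12-month cut-off the shortfall in the mean runs from about 1 month (8.1 against 9) to about 21 months (8.9 against 30). The documents give no re-injection rate, number treated or follow-up time to narrow that range.

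**What to change.** In SAP 9.2, add one descriptive table from the injection records, exempt from the unscheduled-visit exclusion in SAP 5.1. It should show:

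- LOR, glucocorticoid and HA injections per subject and per knee
- subjects with LOR alone and subjects with LOR plus glucocorticoid or HA
- person-months observed

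State there that glucocorticoid and HA given for OA are included. Restore the third secondary objective in SAP 3.1, and amend SAP section 10 so that endpoint 9 is shown as moved to the exposure section rather than cancelled.

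If intervals are reported, censor knees not re-injected at ET and use Kaplan-Meier. If follow-up never allowed a second LOR injection in the same knee, say that no such interval was observable. Do not summarise completed intervals alone.

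The cost is SAP wording and one output, or two if Kaplan-Meier is feasible. Estimates will be imprecise and should be labelled as such.

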10. CHANGES TO PLANNED ANALYSIS

Change	Protocol Section	Rationale
Analysis of the AEs and clinical laboratory evaluations will not be performed. All available safety data will be listed.	10.4.2	Limited available data. See section 8.1 and 8.2.
Analysis of the efficacy endpoints will not be performed. Available efficacy data will be listed.	10.4.3	Study was terminated early.

